6.3.2. Secondary Analysis

As a secondary analysis, the above analysis will be repeated accounting for any baseline imbalances. This will include covariates provided in Section 6.2 that differ across cigarette groups (VLNC, NNC) at baseline with a p-value less than 0.20.

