3.1. Randomization

Randomization will be done in two stages. In the first stage, each individual will be randomized in a 1:1 ratio to either the normal nicotine content (NNC) or the very low nicotine content (VLNC) cigarettes in a double blinded fashion. The randomization will be stratified by gender, menthol status and cigarettes per day (<9, 9+). The goal is 60 subjects per cigarette group. The second randomization stage will be done within the subjects. Individuals in the two cigarette groups will be assigned to all four combinations of sessions involving e-cigs (flavor and nicotine content each at 2 levels) in counter balanced order, which provides 24 possible orders for the four e-cig sessions. The no e-cig session will always be first followed by the e-cig sessions, in an order randomly chosen from one of the 24 possible orders without replacement. Once all 24 session orders have been exhausted, the process will start over with another set of 24 orders. Each cigarette group (n=60) will end up with the same arrangement of the four sessions occurring 2 to 3 times. This will not allow for the evaluation of an order effect in the data analysis, but it will prevent a systematic bias due to the arrangement of the sessions.

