6.2. Describing the Study Population

Demographics and baseline data will be compared between the groups randomized to NNC or VLNC cigarettes. This will include the following: demographic characteristics (age, sex, race, ethnicity, education), tobacco use history (e.g. cigarettes per day, menthol status, vaping frequency, other tobacco product use), TLFB and nicotine dependence (PATH, total score on FTND), etc. Continuous covariates will be summarized by the mean, standard deviation, median and range and compared by two-sample tests (t-test or Wilcoxon rank sum test). Categorical covariates will be summarized by frequencies and percentages and compared using the Chi-squared test or Fisher's exact test, as appropriate.

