6.3.1. Primary Analysis

Descriptive statistics will summarize the number of cigarette puffs by cigarette group and by session. Results will be presented in tabular and graphical format. The primary statistical model will be a linear mixed model (2) carried out according to the 2 x 2 x 2 design, where the between-subject factor is NNC or VLNC cigarettes and the two within-subject factors relate to e-cig flavor (cigarette or non-cigarette flavors) and nicotine content (very low or moderate). The session where no e-cigs are included will be analyzed separately by comparing the normal and reduced nicotine cigarettes groups using linear regression adjusting for baseline CPD from TLFB to improve precision. Sandwich standard

errors will be used to account for potential heteroscedasticity. Data from the four sessions where e-cigs are available will be analyzed using a linear mixed model to account for potential correlation between repeated measures on an individual. The mixed model for the balanced factorial design will allow for the evaluation of the three main effects and their interactions. The major concern for this approach is the occurrence of non-constant variance for the number of cigarette puffs. Therefore, sensitivity analysis will be performed to evaluate the robustness of our assumptions. A generalized estimating equation (GEE) model uses sandwich estimators and thus is less affected by unequal variances, however, is more negatively impacted by the occurrence of missing observations. Additionally, a negative binomial regression approach will check if modeling the number of puffs as count variables provides a better fit to the data. The first mixed model will assume that participant characteristics are balanced between groups due to randomization and include only the three main effects and their interactions along with the stratification variables (gender, menthol status, and CPD [continuous, from the BL TLFB]) and the number of cigarette puffs from session 1 to increase precision.

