6.4. Secondary Endpoint Analysis

Secondary endpoints will be summarized by cigarette group and lab session using the mean and standard deviation. Number of puffs of e-cigs taken are measured in sessions 2 to 5, where e-cigs are available. CO boost (i.e., post-choice CO minus pre-choice CO) is measured at every session (1 to 5). The analysis of the secondary endpoints will be a linear mixed model following the same 2 x 2 x 2 factorial design outlined in section 6.3.1. First with only main effects and interaction terms along with the stratification and the baseline values to increase precision, and then a second model adding in any important baseline characteristics as potential moderators of study outcomes.

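### SAP 6.3.2 picks covariates for the secondary adjusted analysis by a baseline p<0.20 test between randomised arms, so selection takes no account of whether a covariate predicts puffs

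*Combined protocol and SAP*

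**What the plan says.** SAP 6.3.2 states that "As a secondary analysis, the above analysis will be repeated accounting for any baseline imbalances". The selection rule is: "This will include covariates provided in Section 6.2 that differ across cigarette groups (VLNC, NNC) at baseline with a p-value less than 0.20". It gives no criterion based on association with the outcome.

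The candidate pool is in SAP 6.2. It names "demographic characteristics (age, sex, race, ethnicity, education), tobacco use history (e.g. cigarettes per day, menthol status, vaping frequency, other tobacco product use" and then "TLFB and nicotine dependence (PATH, total score on FTND), etc". The last word leaves the pool open. For continuous variables, 6.2 allows either a t-test or a rank-sum test.

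The primary mixed model in SAP 6.3.1 does not use this rule. It fixes its covariates in advance: the factorial terms "along with the stratification variables (gender, menthol status, and CPD [continuous, from the BL TLFB]) and the number of cigarette puffs from session 1". The separate Session 1 regression in 6.3.1 fixes baseline CPD. Under SAP 3.1, "each individual will be randomized in a 1:1 ratio", stratified by gender, menthol status and CPD (below 9, or 9 and above).

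**The concern.** A baseline test between randomised arms asks whether chance produced a difference, and the answer says nothing about whether the variable predicts puffs. Distortion of a treatment contrast by chance imbalance depends on imbalance multiplied by prognostic strength, and the gain in precision from adjustment depends on prognostic strength. The rule looks at imbalance alone. A dependence score with p = 0.25 stays out, while an unrelated variable with p = 0.10 goes in.

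This also departs from the SAP's own reasoning. In 6.3.1 and 6.4, baseline adjustment is justified by precision; only 6.3.2 switches to a significance screen. What is at stake is the efficiency and predictability of one secondary analysis: its covariate set cannot be known until the arms have been compared, and the variables most worth adjusting for will usually be absent.

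**Working it through.** **1. The plan's own figure.** SAP 3.2 gives 60 per group, effect size 0.60, two-sided 0.05 and at least 90% power. The noncentrality is 0.60 × √(60/2) = 3.286 on 118 df, and the noncentral t gives power 0.903. The figure reproduces. It does not depend on the selection rule, but it fixes the setting for step 5.

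**2. How many candidates are new.** Section 6.2 names 12 items: age, sex, race, ethnicity, education, CPD, menthol status, vaping frequency, other tobacco use, TLFB, PATH and FTND. Taking sex as the stratifier gender, three are already in the primary mixed model (sex, menthol, CPD), so 12 − 3 = 9 remain. If TLFB is only the source of CPD, as 6.3.1 suggests, 8 remain. The open end of the list could raise the count.

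**3. Expected selections by chance.** Each passes with probability about 0.20.
- 8 items: 8 × 0.20 = 1.6; chance of at least one, if independent, 1 − 0.8⁸ = 0.832.
- 9 items: 9 × 0.20 = 1.8; chance of at least one, if independent, 1 − 0.8⁹ = 0.866.

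Independence is an assumption, and FTND, PATH and the tobacco-use items are probably correlated. For 8 normal test statistics with a common correlation (assumed), the chance of at least one is between 78% and 79% at 0.3 and about 70% at 0.5. The expected counts do not change.

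**4. Selection ignores prognosis.** Trials were simulated with 60 per arm and one covariate, 20,000 per scenario. The covariate was selected in 19.7% to 20.5% of trials across outcome correlations from 0 to 0.7. A strong predictor is therefore omitted about 80% of the time.

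An omitted imbalance can matter. With 60 per arm, p = 0.25 is a standardised difference of about 1.15 × √(2/60) = 0.21. At an assumed outcome correlation of 0.5, the contrast moves by 0.5 × 0.21 = 0.105 SD, and 0.105/0.60 = 0.175 of the design effect.

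**5. Cost against always adjusting.** Same simulation, one continuous outcome per participant. The documents give no outcome correlations, so a range is shown.

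| Assumed correlation | Power, p<0.20 rule | Power, always adjust | Loss (points) | Type I error, rule | Type I error, always |
|---|---|---|---|---|---|
| 0.3 | 91.2% | 92.7% | 1.5 | 4.5% | 4.8% |
| 0.5 | 92.8% | 96.3% | 3.5 | 3.7% | 5.1% |
| 0.7 | 94.4% | 99.5% | 5.1 | 2.5% | 4.9% |

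The rule is conservative because it leaves the covariate out exactly when the arms are close on it. The unadjusted standard error is then larger than the true variability of the estimate.

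**6. Which effects move.** A participant-level covariate entered as a main effect is constant over the four e-cigarette sessions and cancels from every within-participant contrast. Fitting the 2 × 2 × 2 mixed model to simulated complete data, with and without an imbalanced prognostic covariate, left the flavour, e-liquid nicotine and all interaction estimates identical. Only the cigarette-group main effect changed. Missing sessions could cause small changes elsewhere.

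**The case against.** The strongest case for the plan is that the rule is written in advance, is mechanical, uses baseline data only, and screens a pool that contains plausible predictors ("tobacco use history (e.g. cigarettes per day, menthol status, vaping frequency, other tobacco product use), TLFB and nicotine dependence (PATH, total score on FTND"). It aims at chance imbalance, which is one of the two ingredients of chance bias. The primary model is fixed and already holds the stratifiers and session 1 puffs, probably the strongest predictor of later puffs. The robustness checks named in the SAP are the GEE and negative binomial models in 6.3.1 and the multiple imputation in 6.7; a per-protocol analysis is also planned. None of these uses the rule.

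Most of this stands, and it limits the point to a modest one. It does not rescue the rule, which still ignores the other ingredient, prognosis. Nor is the rule fully mechanical: the pool is open-ended, and the choice between a t-test and a rank-sum test can decide inclusion near 0.20.

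A reader might infer more than the documents support:
- **False positives rise, or the analysis cannot be interpreted.** Step 5 shows the opposite direction of error and a limited loss.
- **All 12 items count, giving 2.4 expected selections and a 93% chance of at least one.** That includes sex, menthol status and CPD, which are already in the model and were stratified.
- **SAP 6.4 has the same fault.** Its second model is described as "adding in any important baseline characteristics as potential moderators of study outcomes". It contains no p<0.20 rule and concerns moderation, a different question.

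**Conclusion.** The point holds, at modest size. The p<0.20 screen selects about 1.6 to 1.8 of the 8 to 9 new candidates by chance, and omits a truly prognostic one about 80% of the time. The consequence is a conservative test and some lost precision for the cigarette-group main effect in one secondary analysis. The primary result and the e-cigarette flavour and nicotine effects are essentially untouched.

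The loss of about 1.5 to 5 power points rests on assumed outcome correlations of 0.3 to 0.7, a single covariate and one outcome per participant. It is probably smaller once CPD and session 1 puffs are in the model, because they would already explain part of what a dependence score or vaping frequency explains. The 83% to 87% chance of at least one selection assumes independent covariates and falls if they are correlated. The 20% selection rate needs only randomisation and no stratification on the covariate.

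**What to change.** In SAP 6.3.2, replace the p<0.20 rule with a closed list of baseline covariates that are already collected and chosen for expected association with puffs. Examples are the FTND or PATH dependence score, vaping frequency and age. Add them to the stratification factors already in the model, and fix the list before unblinding. Keep the group comparisons in 6.2 as description only, with no role in model choice. Leave 6.4 out of this change.

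The SAP is marked finalised on 9/28/2022. If arm-level data have already been seen, report the fixed-list model beside the planned one and label it post hoc.

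The cost is one SAP paragraph and agreement on the list; no new data are needed.

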6.4. Secondary Endpoint Analysis

Secondary endpoints will be summarized by cigarette group and lab session using the mean and standard deviation. Number of puffs of e-cigs taken are measured in sessions 2 to 5, where e-cigs are available. CO boost (i.e., post-choice CO minus pre-choice CO) is measured at every session (1 to 5). The analysis of the secondary endpoints will be a linear mixed model following the same 2 x 2 x 2 factorial design outlined in section 6.3.1. First with only main effects and interaction terms along with the stratification and the baseline values to increase precision, and then a second model adding in any important baseline characteristics as potential moderators of study outcomes.

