the effects of VLNC are influenced by the concurrent availability of e-cigs varying in **nicotine concentration and flavors**. These procedures involve a sampling phase, in which the participant samples and rates the two options, followed by choice (preference) phase, consisting of a series of discrete trials in which the participant can choose between the two options (or choose to forgo either option). The option that is chosen more often is considered to have greater relative reinforcing efficacy (Comer et al., 2008). In addition to having strong internal and predictive validity (Carter et al., 2009), choice procedures have ecological validity as they mimic situations in which smokers choose which product to buy or use among those concurrently available in the natural environment. We considered a free-access procedure in which both options are made concurrently available and *ad libitum* consumption is measured, however choice procedures are generally more sensitive than free access procedures to differences among reinforcers (e.g., Griffiths et al., 1986; Shahan et al., 1999). Participants will complete **six sessions**, including the **Screening/Baseline (BL)** session, during which eligibility will be confirmed and background questionnaires will be completed. Participants will then complete five lab sessions, a minimum of 48 hours apart; each session will follow overnight smoking abstinence.

In **Lab Session 1**, only combusted cigarettes (either NNC or VLNC) will be available. This session will always occur first because, conceptually, the no-e-cig session is the baseline condition in this study; scheduling this session first ensures that smoking choices in this condition will not be affected by any potential carryover effects of e-cig exposure on smoking choices. During the sampling phase of the choice procedure ("Preference Task"), participants will sample and then rate the cigarette using the Product Rating forms. In the preference phase, participants will be prompted via computerized instructions to make a series of 10 choices. Each choice will be to either take 2 cigarette puffs or to abstain from puffing; a total of 20 cigarette puffs is available. After completing the choice task, participants will practice using the vaping devices and sample the e-liquid flavors available. They will select which cigarette and non-cigarette flavored e-liquids they want to use during Sessions 2-5.

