- 1) Identifying Information Form will include the participant's Subject Identifier, name, address (including the county of residence), email address, phone number, age, and date of birth.
 - a. This form will be entered into the 'Identifying Information Access Database'.
 - i. Identifying information will be kept in a locked file cabinet (source document) and in a password protected Access Database (electronic version) separate from all other study data.

The following screening assessments will be administered as an interview and entered into REDCap by the interviewer:

- 1) Brief Medical History Questionnaire to query current diagnoses, symptoms and past health problems.
 - a. Sections of the questionnaire will be entered into REDCap.
 - b. The medications section will be transferred to the 'Concomitant Medications' form in REDCap.
- 2) Medical History Follow-Up Questionnaire, if applicable, to further query current diagnoses, symptoms and past health problems.
 - a. This questionnaire is entered as a pdf and sent to Licensed Medical Provider (LMP). It will be a source document only and will not be used as data.
- 3) The Mini International Neuropsychiatric Interview (MINI) suicide subscale (Sheehan et al., 1997) to evaluate suicide risk.
- 4) Tobacco Use History and Exposure Questionnaire, which measures variables such as smoking amount, cigarette brand, age of initiation of smoking, number of quit attempts, duration of quit attempts and duration of smoking.
- 5) Vaping History Questionnaire will assess lifetime and past 30-day use of vaping devices as well as information about the devices and e-liquids used.
- 6) Drug Use Questionnaire, which measures illicit drug use during the past 30 days.
- 7) Timeline Follow Back (TLFB) Questionnaire, which will assess past 14-day tobacco and nicotine product use as well as alcohol and marijuana use. If a participant's reported cigarette or vaping use on the TLFB conflict with their reporting on the Tobacco Use History and Exposure Questionnaire, the RA will point out the discrepancy to the participant and ask whether they would like to modify their responses on the Tobacco Use History and Exposure Questionnaire or clarify why they are discrepant (e.g., participants had an upper respiratory infection in the past week that resulted in atypical smoking behavior).

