Those with unstable medical or psychiatric conditions are excluded as these symptoms could affect a participant's ability to complete the study. Examples include but are not limited to the following: angina, stroke, heart attack, blood clots in the arms or legs for which the individual is undergoing active medical treatment, cancer requiring active chemotherapy or radiation therapy, severe shortness of breath caused by conditions such as uncontrolled asthma, COPD, or arrhythmia, active untreated infection such as pneumonia, active untreated endocrine disorder such as hyperthyroidism. The LMP can also exclude participants for conditions in which participation is likely to pose a significant threat to health or for which the condition could interfere with the ability of the participant to fully participate. We will exclude those indicating immediate readiness to stop smoking or plans to quit in the next 30 days, as participation in this study may not lead to reductions in smoking. We will exclude pregnant and breastfeeding women due to the potential harmful effects of tobacco use on developing fetuses and infants. Anyone with current or recent alcohol or drug abuse problems as these factors could independently affect smoking behavior during the study. Individuals with baseline CO readings greater than 80 ppm, those with heart rate or blood pressure readings that are out of range, those with allergies to propylene glycol/vegetable glycerin/nuts/chemical food flavorants and anyone who has attempted suicide in the past two years will be excluded from the study for safety concerns. If an individual has recently participated in a smoking research study that changed his/her smoking behavior this person would be excluded because he/she would not have a stable smoking baseline. Because participants are required to complete portions of the protocol independently in the lab, they will need to be able to independently read and comprehend the study materials. Daily vaping device users are not excluded and individuals must have tried vaping devices on two or more occasions in their lifetime in order to minimize concerns about introducing a novel nicotine product to those who have not previously used it.

Potential risks of participation

- 1) **Survey Questionnaires:** The interview will include questions about medical history, drug and alcohol use, and questionnaires about mood. Answering these personal questions could make the participant

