In the *Sampling Phase* (~20 min), participants will be oriented to task procedures and shown the products available for that session. In Lab Session 1, only one product - NNC or VLNC cigarettes - will be available. Once the task begins, all instructions will be delivered via computer; sessions will be continuously observed by a research assistant through a one-way mirror. Participants will be prompted via computerized instructions to take four timed puffs of the cigarette and then complete the Product Rating forms (see description below). There will be a 15-min delay prior to the *Preference Phase*. During protocol breaks, participants will be allowed to watch TV or read magazines.

Product Rating Forms will be administered using Qualtrics or REDCap immediately after sampling the product:

- 1) MNWS
- 2) QSU-10 Usual Brand Version
- 3) PANAS
- 4) CES- Study Cigarette Version
- 5) PHRS- Study Cigarette Version
- 6) Cigarette Purchase Task –Study Cigarette Version

Preference Phase Procedures

After the *Sampling Phase* has been completed, participants will complete the *Preference Phase* (30 min), which is designed to determine the relative reinforcement value of each product. During this phase, participants undergo a series of 10 choice trials, each lasting 1 minute, with a 2-min inter-trial interval. During each trial, participants will be presented (via computer) with a choice between taking 2 puffs of the cigarette or to abstain from puffing. Indices derived from this task include: total number of cigarette puffs; and total number of choices to abstain from product use. The maximum puffing rate for this task is 20 puffs in 30 minutes.

POST-TASK Physiological measures collected, recorded on paper, and entered into REDCap by the interviewer at the end of the visit:

- 1) CO

Vaping Device Practice

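### SAP 6.4 adjusts e-cig puffs for a baseline value that this endpoint does not have; pre-randomisation vaping frequency could take its place

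*Combined protocol and SAP*

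**What the plan says.** SAP 6.4 covers two secondary endpoints, e-cig puffs and CO boost, with a single model description that refers back to the factorial design in 6.3.1. The first model is described as: "First with only main effects and interaction terms along with the stratification and the baseline values to increase precision". A second model may then add baseline characteristics judged important, framed as potential moderators; 6.4 gives no rule for choosing them.

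The same section states when e-cig puffs exist: "Number of puffs of e-cigs taken are measured in sessions 2 to 5, where e-cigs are available". It says that CO boost is measured at all five sessions. For the primary endpoint, 6.3.1 names its precision covariate outright: "the number of cigarette puffs from session 1 to increase precision".

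On Session 1, the protocol's Overall Study Design says "only combusted cigarettes (either NNC or VLNC) will be available", and its Lab Session 1 Procedures say the same of the sampling phase: "In Lab Session 1, only one product - NNC or VLNC cigarettes - will be available".

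On vaping history, the protocol's rationale for the exclusion criteria says: "Daily vaping device users are not excluded and individuals must have tried vaping devices on two or more occasions in their lifetime". Under Screening Procedures, "Vaping History Questionnaire will assess lifetime and past 30-day use of vaping devices", and the baseline TLFB covers nicotine product use over the previous 14 days. SAP 6.2 lists vaping frequency among the baseline variables to be described and compared. SAP 3.1 stratifies on gender, menthol status and cigarettes per day, not on vaping.

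**The concern.** The baseline term is in the model to gain precision. For e-cig puffs there is nothing to put in it, so whoever runs the analysis must drop it, substitute Session 1 cigarette puffs by analogy with 6.3.1, or pick something else. These choices give different models, and the SAP does not decide between them.

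Enrolment runs from two lifetime uses of a vaping device to daily vaping. Prior vaping is thus a natural candidate predictor of how often a participant chooses the e-cig, and it is recorded before allocation. As written, it reaches the e-cig-puff analysis only through the second model, at the analyst's discretion. At stake is avoidable between-participant noise in the VLNC-NNC comparison of e-cig puffs, and a covariate choice left open for a secondary endpoint.

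**Working it through.** **Step 1. Is there a baseline value?**

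| Occasion | E-cig puffs in a choice task | CO boost |
|---|---|---|
| Screening/Baseline | No: no preference task | No |
| Session 1 | No: cigarette or abstain only | Yes |
| Sessions 2-5 | Yes (outcome) | Yes (outcome) |

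The vaping practice and flavor sampling that close Session 1 use 0 mg/ml liquid and are not a choice task, and no puff count from them is defined as a measure. The protocol's measures table seems to mark e-cig choices at Session 1, but that row may have been damaged in text extraction. The protocol's design and Session 1 text, and SAP 5.1 and 6.4, all agree that there is no e-cig choice in that session.

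**Step 2. Would Session 1 cigarette puffs do?** Lab Session 1 Procedures place randomisation to VLNC or NNC during that session, and the Session 1 task uses the assigned cigarette. Session 1 cigarette puffs are therefore post-randomisation and may themselves respond to the allocation. Adjusting e-cig puffs for them could absorb part of the VLNC-NNC effect being estimated.

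**Step 3. Reproduce the planned power.** Inputs from SAP 3.2: n = 60 per arm, effect size 0.60, two-sided alpha 0.05. The noncentrality is 0.60 × √(60/2) = 3.286. Power is 90.3% by the noncentral t with 118 df, or 90.8% by the normal approximation. The stated minimum of 90% is reproduced, and it uses no covariate.

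**Step 4. Effect of a participant-level covariate.** Let r be the partial correlation of baseline vaping frequency with a participant's mean e-cig puffs, given the stratification variables. The documents give no value, so r is assumed. The variance of the arm contrast is multiplied by 1 − r², the equivalent sample size is 60/(1 − r²), and the standardised effect becomes 0.60/√(1 − r²).

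| Assumed r | Variance reduction | Equivalent n per arm | Power at ES 0.60 (noncentral t) |
|---|---|---|---|
| 0 | 0% | 60 | 90.3% |
| 0.1 | 1% | 60.6 | 90.6% |
| 0.3 | 9% | 65.9 | 92.7% |
| 0.5 | 25% | 80.0 | 96.4% |

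The effect size detectable with 90% power (normal approximation) is (1.960 + 1.282) × √(2/60) × √(1 − r²). That is 0.592 at r = 0, 0.565 at r = 0.3 and 0.513 at r = 0.5.

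**Step 5. Which contrasts gain?** Flavor and e-liquid nicotine are compared within participants, so a covariate that is constant within a participant adds little there. The gain belongs to the between-arm contrast.

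**The case against.** The best defence is that one sentence serves two endpoints, one of which does have a Session 1 value, and that 6.4 points back to 6.3.1, where the precision covariate is Session 1 cigarette puffs. On that reading the e-cig-puff model can be fitted. This stands in part: it would be wrong to infer that no analysis of e-cig puffs is possible. But 6.4 does not state that reading, and Step 2 shows why it is a poor one.

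It is also fair to say that adjusting for the stratification factors alone is defensible, that randomisation protects against systematic bias, and that chance imbalance in vaping is already reflected in the standard error. All of that stands, and it limits the point to precision and pre-specification.

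A reader might go further and infer that the primary cigarette-puff model in 6.3.1 has the same gap. The documents do not support that. The 6.3.1 model already has a named, available Session 1 covariate; whether a post-randomisation covariate is suitable there is a separate question. SAP 6.3.2 also repeats that analysis with any 6.2 covariate differing between arms at p < 0.20, and vaping frequency is in the 6.2 list. With 60 per arm that rule is triggered by a difference of about 1.282 × √(2/60) = 0.23 SD. Nor do the documents show that frequent vapers choose cigarettes less often in this task.

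A reader might also infer that the arm comparison is underpowered without the covariate. An effect size of 0.5 would suggest so, but SAP 3.2 uses 0.5 only for the within-subject factors. The arm contrast is sized at 0.60, where power is already 90%.

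**Conclusion.** The point holds for one endpoint and one model term. The precision covariate that SAP 6.4 calls for does not exist for e-cig puffs, and this follows from the text without any assumption. The more obvious stand-in is measured after randomisation, while a pre-randomisation candidate is already collected and listed in 6.2.

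The size of the benefit does rest on an assumption. For partial r from 0.1 to 0.5 the arm-contrast variance falls by 1% to 25%. At the planned effect size, power rises by 0.3 points (90.3% to 90.6%) at r = 0.1, which is negligible, and by about 6 points (90.3% to 96.4%) at r = 0.5. No stated figure in the plan is invalidated and no bias is implied. The change is worth making because it closes an undefined term at almost no cost.

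**What to change.** In SAP 6.4, define the baseline covariate separately for each secondary endpoint:

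- **E-cig puffs:** replace the general reference to baseline values with baseline vaping frequency, defined as the number of days vaped in the 14-day baseline TLFB, entered as a continuous fixed covariate in the first model.
- **CO boost:** if the Session 1 value is intended, say so, and note that it is measured after randomisation.

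Leave the 6.3.1 cigarette-puff model as it is; a version that adds vaping frequency could be offered as a labelled sensitivity analysis. If the e-cig-puff analysis has already been run, report which covariate was used and add the vaping-adjusted model as a labelled sensitivity analysis.

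The cost is one SAP sentence per endpoint and one degree of freedom in the e-cig-puff model. No new data are needed.
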